9.2.2. Immunogenicity Subset

All participants included in the Immunogenicity Subset (N = 400) will be added randomly during Stage 2 of the double-blind phase of the study. Healthy adults and elderly will be assigned to subset 1a and 1b respectively, while adults and elderly with comorbidities will be assigned to subset 2a and 2b respectively, with approximately 100 participants per group as displayed in [Table 3](#).

A sample size of 400 participants, distributed as described in [Table 3](#), is estimated to be sufficient to allow robust description of immune responses to Ad26.COV2.S vaccine. These numbers are expected to provide a solid understanding of the magnitude and kinetics of the humoral response induced by the Ad26.COV2.S vaccine.

9.2.3. Immunogenicity Correlates (Correlates Subset)

Correlates will be assessed in a subset where immune responses and/or transcriptome modifications are measured in all vaccine recipients who experience a SARS-CoV-2 event, and in random samples of vaccine recipients who have not been infected, in a 1:5 ratio. The goal of this case control study is to assess correlates of risk of SARS-CoV-2 infection (and potential other secondary endpoints) in the vaccine group by comparing vaccine-induced immune responses and transcriptome modifications associated with COVID-19. Also, placebo participants will be included in this subset (placebo infected, seropositive [based on N-protein] non-infected and seronegative non-infected), if feasible.

Correlates will also be investigated via a case-cohort design, including measurement of immunological markers in a random subcohort augmented by infected and symptomatic cases.

Placebo controls will be matched with cases from the same stage (comorbidities), age, and other co-factors as deemed appropriate. These will be detailed in the Correlates SAP.

9.2.4. Safety (Safety Subset)

While mild to moderate reactogenicity (local injection site and systemic reactions) are expected, AEs that preclude further vaccine administration (if applicable) are not anticipated.

Unsolicited AEs will be captured for a period of 28 days after each vaccination. Solicited and unsolicited AEs will be captured in the Safety Subset, ie, approximately 6,000 participants (~3,000 from the active group, ~3,000 from the placebo group; and including at least 2,000 from the older age group [≥ 60 years of age] if feasible).

AESIs (from Protocol Amendment 5), and SAEs will be captured in all participants and throughout the study. MAAEs (including new onset of chronic diseases) will be captured in all participants until 6 months after the last double-blind or open-label vaccination (including the open-label vaccination or booster vaccination, whichever comes last), except for MAAEs leading to study discontinuation, which are to be reported during the entire study. Based on a sample size of approximately 30,000 participants, and approximately 15,000 in the active vaccination group, for SAEs, the observation of 0 events in the database would be associated with 95% confidence that

the true rate is less than 0.01%. [Table 6](#) shows the probabilities of observing at least 1 event (solicited, unsolicited, or SAE) in 1 of the groups at given true AE rates.

Table 6: Probability of Observing at Least 1 Adverse Event or Serious Adverse Event at a Given True Adverse Event Rate in the Active Group (With a Total Sample Size of Approximately 30,000 Participants)

True AE Rate	Probability of Observing at Least 1 Adverse Event in the Active Group in N Participants	
	Solicited/Unsolicited AEs N=3,000	SAEs N=15,000
0.01%	26%	78%
0.1%	95%	100%
≥0.5%	100%	100%

AE = adverse event; N = number of participants receiving study vaccine (Ad26.COV2.S or placebo); SAE = serious adverse events

The aim is to recruit up to 6,000 participants in the Safety Subset. At the time of writing the Protocol Amendment 4, the target recruitment has not been completed yet. Every effort will be made to reach the target of 6,000 participants, but the final number of participants recruited in the Safety Subset may be less due to unblinding of the participants. After an individual participant has been unblinded, he/she is no longer considered as part of the Safety Subset and no further solicited/unsolicited symptoms that are specific to the Safety Subset will be collected. All other safety reporting requirements applicable for all participants will be maintained (Section [8.3.1](#)).

As of Amendment 7, a passive follow-up approach is adopted: follow-up visits or phone calls by the site at scheduled time points to collect information on any protocol-required safety assessment (see Section [8.3.1](#)).

In addition, SAEs, AEs, and MAAEs related to COVID-19 need to be reported together with the concomitant medications related to these events until study end. Any confirmatory COVID-19 laboratory information should be reported in the eCRF.

Populations for Analysis Sets

For purposes of analysis, the following populations are defined:

Full Analysis Set (FAS): All randomized participants with at least 1 documented study vaccine administration, regardless of the occurrence of protocol deviations and serostatus at enrollment. Analyses of safety will be performed on the FAS. Vaccine efficacy analyses can be repeated using the FAS.

Safety Subset: subset of the FAS for the analysis of solicited and unsolicited AEs.

Per-protocol Efficacy (PP) population^a: Participants in the FAS who receive 2 doses of study vaccine and who are seronegative at the time of 1st vaccination and at Day 71, and who have no other major protocol deviations that were judged to possibly impact the efficacy of the vaccine before unblinding. The PA of VE will be based on the PP population. In the double-blind phase, the PP will be the main analysis population for efficacy analyses.

Per-protocol Immunogenicity (PPI) population^a: All randomized participants who receive 2 doses of study vaccine in the double-blind phase, including those who are part of the Immunogenicity Subset and for whom immunogenicity data are available, excluding participants with major protocol deviations expected to impact the immunogenicity outcomes. In addition, for participants who experience a SARS-CoV-2 event (molecularly confirmed), samples taken after the event and samples taken outside protocol windows will not be taken into account in the assessment of the immunogenicity. The PPI population is the primary immunogenicity population. For key tables, sensitivity immunogenicity analyses will also be performed on the FAS, including participants who are part of the Immunogenicity Subset for whom immunogenicity measures are available. Excluded samples might be taken into account as well in the sensitivity analysis. Analyses of vaccine immunogenicity and immune correlates of risk will be based on PPI.

The populations for the open-label active and open-label passive follow-up phase are described in the SAP.

The list of major protocol deviations to be excluded from the efficacy for the double-blind analysis and/or immunogenicity analyses will be specified in the SAP and/or this list will be reported into protocol deviation dataset of the clinical database before database lock and unblinding.

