9.2. Sample Size Determination

9.2.1. Efficacy (Total Sample Size)

For the double-blind phase, the sample size is determined using the following assumptions:

- a VE for molecularly confirmed, moderate to severe/critical SARS-CoV-2 infection of 65%.
- type 1 error rate $\alpha = 2.5\%$ to evaluate VE of the vaccine regimen.
- a randomization ratio of 1:1 for active versus placebo

Events are defined as first occurrence of molecularly confirmed, moderate to severe/critical COVID-19 according to the case definition in Section 8.1.3.1 in the PP population at least 14 days after the second vaccination with study vaccine (Day 71).

Under the assumptions above, a total of 104 events will provide approximately 90% power to reject the null hypothesis of $H_0: VE \leq 30\%$, according to the primary endpoint case definition of moderate to severe/critical COVID-19 (Section 8.1.3.1).

If the primary hypothesis testing is successful, secondary objectives will be evaluated against a null hypothesis employing a lower limit $VE > 0\%$. The method to perform hypothesis testing of primary and secondary objectives preserving the FWER will be specified in the SAP. The FWER will be controlled at 2.5%.

Sample Size Justification

Based on the variations in seroprevalence, degree of social distancing and use of personal protective equipment, it is not feasible to estimate the incidence rates that can be attained at the time of the start of this study. It is also unknown which local regulations (eg, potential lockdowns) will be in effect at that time.

The sample size is approximately 15,000/group (approximately 30,000 in total) and is determined based on estimated annualized incidence rate of moderate to severe/critical COVID-19 of 1% to 4% at the start of the study.

Assuming 2 months of recruitment and 10% seroprevalence, the selected sample size will have a high probability (approximately 90%) to have reached an efficacy signal within 15 months after first participant vaccinated for an assumed $VE \geq 65\%$ under an assumed incidence of 1.4% in Month 1-3, and waning of incidence thereafter, eg, 50% reduction at Month 4 (0.70% annualized) followed by further reduction to 0.58%.

With higher incidences at the start of the study, the timelines to efficacy will shorten.

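### Zero SAEs among 15,000 vaccinees excludes a rate of 0.02%, not the 0.01% stated in Protocol Section 9.2.4, and Table 6 in the same section shows it

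*Protocol*

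**What the plan says.** Section 9.2.4 of the Protocol describes what the safety database can show. The sentence on SAEs opens with the total, "Based on a sample size of approximately 30,000 participants", and then narrows to "approximately 15,000 in the active vaccination group, for SAEs". It goes on to say that "the observation of 0 events in the database" "would be associated with 95% confidence that" "the true rate is less than 0.01" per cent. It does not say whether the 95% is one-sided or two-sided.

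Table 6 comes next. Its column heading is "Probability of Observing at Least 1 Adverse Event in the Active Group in N Participants", with N = 3,000 for solicited and unsolicited AEs and N = 15,000 for SAEs. At a true rate of 0.01% it lists 26% and 78%; at 0.1%, 95% and 100%; at 0.5% or more, 100% in both columns.

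Section 9.2.1 gives the allocation as "a randomization ratio of 1:1 for active versus placebo". The introduction to Section 9 states that Sections 9.2 to 9.6 apply to the double-blind phase.

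**The concern.** The sentence and the table use the same active-group denominator for SAEs and give incompatible answers. Confidence that a rate lies below some value after zero events equals the probability of seeing at least one event at that value. Table 6 puts that probability at 78% for 0.01%; the sentence claims 95%.

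The sentence tells investigators, ethics committees and regulators how rare a serious harm the vaccinated group can exclude. Section 9.6 plans no formal testing of safety data, so this statement and Table 6 are the section's quantitative account of safety resolution. Rare serious harm is also a live matter in this trial: Section 8.3.7.1 makes thrombosis with thrombocytopenia syndrome an AESI and describes it as very rare.

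**Working it through.** **Inputs.** Total about 30,000, active group about 15,000, 0 events, 95% confidence, stated bound 0.01% (all Section 9.2.4); 1:1 allocation (Section 9.2.1); up to 10% additional recruitment (Section 9.2.1). The 95% is read as one-sided, the natural reading for an upper bound; the two-sided result is shown as well.

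**Step 1: reproduce the stated figure.** With 0 events in N, the exact one-sided 95% upper bound is 1 − 0.05^(1/N).

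- N = 30,000: 1 − 0.05^(1/30,000) = 0.009985%. The rule of three gives 3/30,000 = 0.0100%.

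So 0.01% is obtained when both arms are counted. The smallest N that reaches it is ln(0.05)/ln(1 − 0.0001), which rounds up to 29,956.

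**Step 2: use the active group.** For N = 15,000:

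| Method | Formula | Upper bound |
|---|---|---|
| Exact, one-sided 95% | 1 − 0.05^(1/15,000) | 0.01997% |
| Rule of three | 3/15,000 | 0.0200% |
| Poisson, one-sided 95% | −ln(0.05)/15,000 | 0.01997% |
| Clopper-Pearson, two-sided 95% | 1 − 0.025^(1/15,000) | 0.0246% |

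These correspond to about 1 in 5,000 (one-sided) and 1 in 4,070 (two-sided). None of these methods gives 0.01% at this N.

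**Step 3: check against Table 6.** The probability of at least one event is 1 − (1 − p)^N.

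| True rate | N = 3,000 | N = 15,000 |
|---|---|---|
| 0.01% | 25.9% | 77.7% |
| 0.1% | 95.0% | 100% |
| 0.5% | 100% | 100% |

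Every cell matches the printed table, so the table is right and the sentence is wrong. At 0.01% and N = 15,000, the probability of zero events is (1 − 0.0001)^15,000 = 0.223. Zero events therefore supports a rate below 0.01% with 77.7% confidence.

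**Step 4: check the correction by the table's own method.** At a true rate of 0.02% and N = 15,000, the probability of at least one event is 95.02%, which agrees with a 95% bound of 0.02%.

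**Step 5: sensitivity.** With the full 10% over-recruitment the active group would be 15,000 × 1.10 = 16,500, and the bound 1 − 0.05^(1/16,500) = 0.0182%. The stated figure is still not reached.

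**The case against.** The best defence is that the denominator is ambiguous rather than the arithmetic wrong. The sentence begins with the total of 30,000 and speaks of the database as a whole, and a footnote to Table 6 defines N as recipients of active vaccine or placebo. With 30,000 the one-sided bound does come to 0.01%. This probably explains where the number came from. It does not make it usable: half of those participants receive placebo, the sentence itself names the 15,000 in the active group, and the table heading is confined to that group. A rate pooled over both arms does not bound the rate under vaccine.

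A second defence is crossover. Placebo recipients are offered the vaccine at the unblinding visit and SAEs are collected throughout, so more than 15,000 people may eventually contribute vaccinated follow-up. That is true of the study as a whole, but Section 9 ties Section 9.2 to the double-blind phase, where the active group is about 15,000.

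Third, the consequence is limited. Safety is analysed descriptively, the efficacy sample size rests on 104 events, and neither the pausing rules nor the harm boundaries use the figure. The correct detection probability is also printed just below, so a careful reader can find it. All of this stands. It bears on how much damage the error does, not on whether the number is wrong.

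**Conclusion.** The point holds. For about 15,000 vaccinees in the double-blind phase, zero events of an SAE excludes a true rate of 0.020% with one-sided 95% confidence (0.025% two-sided). The stated 0.01% carries about 78% confidence. The sentence overstates the safety resolution by a factor of two on the one-sided reading, and by about 2.5 on the two-sided reading. The conflict with Table 6 needs no assumption about sidedness or outside data. The error sits in a descriptive precision statement: no hypothesis test, efficacy sample size or stopping boundary in the protocol text reviewed depends on it.

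**What to change.** In Section 9.2.4, change the bound from 0.01% to 0.02% and attach it to the right denominator, for example: if no SAE is seen among the roughly 15,000 active-group participants, the one-sided 95% upper confidence limit for the true rate is 0.02%. Drop the reference to the 30,000 total from that sentence, or keep it only to describe the trial's size. Table 6 needs no change and will then agree with the text.

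If a pooled figure was really intended, the text should say that 0.01% refers to both arms combined, and still give 0.02% for vaccinees. Any repeat of the sentence elsewhere, including in the SAP, should carry the same correction. The cost is one figure and a less favourable, but accurate, claim.

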7. DISCONTINUATION OF STUDY VACCINATION AND PARTICIPANT DISCONTINUATION/WITHDRAWAL

7.1. Discontinuation of Study Vaccination

Study vaccinations in the double-blind phase will be withheld for the reasons listed below. These participants must not receive any further doses of study vaccine but should remain on study for follow-up with assessments of safety, efficacy, and immunogenicity as indicated in the [Schedules of Activities](#). Additional unscheduled visits may be performed for safety/reactogenicity reasons, if needed. In case of questions, the investigator is encouraged to contact the sponsor.

- Any related AE, worsening of health status or intercurrent illnesses that, in the opinion of the investigator, requires discontinuation from study vaccine
- The participant becomes pregnant
- Unblinding on the participant level that, in the opinion of the sponsor, would compromise the integrity of the data
- Unblinding requested by a study participant in order to receive an authorized/licensed COVID-19 vaccine prior to general unblinding at the time of EUA in the US for the single-dose schedule of Ad26.COV2.S
- Anaphylactic reaction following vaccination, not attributable to causes other than vaccination
- SAE or other potentially life-threatening (Grade 4) event that is determined to be related to study vaccine
- Chronic or recurrent use of systemic corticosteroids and administration of antineoplastic and immunomodulating agents or radiotherapy
- Participant received any experimental medication (including experimental vaccines other than the study vaccine) or received a COVID-19 vaccine or treatment
- Withdrawal of consent to receive further study vaccination
- Participant has a molecularly confirmed SARS-CoV-2 infection based on samples collected within the study (see Section [8.1.2](#))
- Participant previously experienced TTS or HIT.

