8.1.4. Immunogenicity Assessments

Up to Protocol Amendment 7, blood will be collected from all non-Immunogenicity Subset participants for humoral immunogenicity assessments at Day 1 (before the 1st vaccination), 14 days, 6 months and 1 year after the second vaccination.

In the double-blind phase, for a total of approximately 400 participants in the Immunogenicity Subset, blood will be collected for analysis of humoral immune responses before each vaccination, 28 days after the 1st vaccination and 14 days, 6 months, 1 year, 18 months, and 2 years after the second vaccination.

For a total of approximately 400 participants in the new Immunogenicity Subset, blood will be collected for analysis of humoral immune responses at baseline and at Day 71, Week 32, and Week 60 after the first vaccination.

All participants in the Immunogenicity Subset will be enrolled from Study Stage 2. Participants in the Immunogenicity Subset in the double-blind phase and in the open-label phase (referred to as Subset "B") will be divided into 4 groups as presented in [Table 3](#) and [Table 4](#), respectively.

Table 3: Sample Size and Distribution of the Immunogenicity Subset Between Active and Placebo Groups

Study Vaccine	Subset 1a	Subset 1b	Subset 2a	Subset 2b
5×10 ¹⁰ vp/5×10 ¹⁰ vp	50	50	50	50
Placebo/placebo	50	50	50	50
Total	100	100	100	100

vp virus particles

Subset 1a: healthy participants ≥18 years to <60 years of age without relevant comorbidities, enrolled during Stage 2.

Subset 1b: healthy participants ≥60 years of age without relevant comorbidities, enrolled during Stage 2.

Subset 2a: participants ≥18 to <60 years of age with relevant comorbidities, enrolled during Stage 2.

Subset 2b: participants ≥60 years of age with relevant comorbidities, enrolled during Stage 2

Table 4: Sample Size and Distribution of the Immunogenicity Subset B for the Open-label Phase

Study Vaccine	Subset B1a	Subset B1b	Subset B2a	Subset B2b
5×10 ¹⁰ vp, 5×10 ¹⁰ vp	50	50	50	50
5×10 ¹⁰ vp	50	50	50	50
Total	100	100	100	100

vp virus particles

Subset B1a: healthy participants ≥18 years to <60 years of age without relevant comorbidities.

Subset B1b: healthy participants ≥60 years of age without relevant comorbidities.

Subset B2a: participants ≥18 to <60 years of age with relevant comorbidities.

Subset B2b: participants ≥60 years of age with relevant comorbidities.

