Participants initially enrolled in the Ad26.COV2.S group during the double-blind phase who will not receive a second vaccination (refer to Section 6.4) will be assured they received the dose level that was submitted for EUA (single-dose schedule of 5×10^{10} vp Ad26.COV2.S), and will be asked to continue to be followed in this study in line with the Schedule of Activities Section 1.3.3.

Investigators will be encouraged to follow health authority guidelines on prioritization of immunization. Investigators are encouraged to consider current local public health guidance for determining the scheduling priority of participants. For example, participants with comorbidities and/or of specific age groups can be scheduled prior to participants without comorbidities if this is in line with local guidance. This should be done in a blinded way, ensuring that participants who were not previously unblinded for other reasons are not unblinded until the unblinding visit. All participants will be counselled to continue practicing other public health/preventive measures that were introduced at the start of this pandemic (eg, social distancing, face masks, frequent hand washing), in compliance with local and national guidelines.

8.9. Assessment and Procedures for Booster Vaccination and Follow-up After Implementation of Protocol Amendment 6

As of Protocol Amendment 7:

No further booster doses will be administered after implementation of Protocol Amendment 7, except if there is a medical reason or if there is a non-availability of other vaccines to the participant. The investigator should inform participants on the availability of other COVID-19 vaccines.

Up to Protocol Amendment 7:

With implementation of Protocol Amendment 6, all ongoing participants who received only a single vaccination with Ad26.COV2.S in the study will be offered a single booster dose of Ad26.COV2.S vaccine under the conditions delineated in Section 6.5. Participants who already received 2 vaccinations with Ad26.COV2.S at the 5×10^{10} vp dose level or any COVID-19 vaccinations outside of the study (including the Janssen vaccine) at the time of local approval of Protocol Amendment 6 are not eligible to receive a booster vaccination with Ad26.COV2.S.

Eligible participants who consent to receive the booster vaccination will follow the schedule as presented in Section 1.3.5. The following assessments will be performed before booster

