9.5. Immunogenicity Analyses

For the double-blind phase, no formal statistical testing of the immunogenicity data is planned. All immunogenicity analyses will be performed on the PPI set. Key tables might be repeated for the FAS (including samples that are excluded from the PPI analysis). For the open-label phase and passive follow-up phase, no statistical testing of the immunogenicity data is planned. All details regarding the analysis and will be described in the SAP.

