9.5.1. Immunogenicity Subset

No formal hypothesis on immunogenicity will be tested. Descriptive statistics (eg, geometric mean and 95% confidence interval for the neutralization assay and ELISA) will be calculated for continuous immunologic parameters at all timepoints. Geometric mean fold rises from baseline and corresponding 95% confidence intervals might additionally be calculated. Baseline is considered as the last available assessment before vaccination. Graphical representations of immunologic parameters will be made as applicable.

The impact of baseline factors on the humoral responses will be explored graphically or via descriptive statistics. In addition, in a subset of 400 participants (the Immunogenicity Subset; ~200 from the active group, ~200 from the placebo group), humoral immunogenicity samples are taken on more occasions.

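### The per-protocol immunogenicity set requires dose 2 even for samples drawn before dose 2, so the primary post-dose-1 summaries depend on a later event

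*Protocol*

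**What the plan says.** The population definitions that follow Section 9.2.4 of the protocol describe the PPI population as "All randomized participants who receive 2 doses of study vaccine in the double-blind phase", less those with major deviations expected to affect immunogenicity. The same paragraph states that "The PPI population is the primary immunogenicity population". Section 9.5 adds that "All immunogenicity analyses will be performed on the PPI set", and Section 9.5.1 says that descriptive statistics "will be calculated for continuous immunologic parameters at all timepoints".

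Section 8.1.4 sets the sampling for the double-blind Immunogenicity Subset: "blood will be collected for analysis of humoral immune responses before each vaccination, 28 days after the 1st vaccination", then 14 days after dose 2 and at later visits. With dose 2 at Day 57, the two samples at issue fall at about Day 29 and Day 57.

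Section 7.1 lists reasons for withholding further doses in the double-blind phase, among them a related adverse event, pregnancy, confirmed infection and unblinding. Such participants "should remain on study for follow-up with assessments of safety, efficacy, and immunogenicity". Section 8.8 also foresees "Participants initially enrolled in the Ad26.COV2.S group during the double-blind phase who will not receive a second vaccination".

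The PPI paragraph contains one sample-level rule: after a confirmed infection, later samples are dropped, as are samples outside the protocol windows. It contains no comparable rule for a missed dose 2. It also provides an FAS sensitivity analysis for key tables. That paragraph states the FAS analysis as certain; Section 9.5 states it only as possible.

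**The concern.** Whether a participant's Day 29 or pre-dose-2 sample enters the primary summary is decided by whether dose 2 is given afterwards. At the moment the sample is drawn, a participant with one dose and no deviation has followed the protocol fully. Two things can go wrong.

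- **Precision.** Usable results are left out, and the strata are small: 50 vaccinees in each of the four groups in Table 3.
- **Selection.** Some reasons for withholding dose 2 may be linked to the response being measured. A related adverse event is a consequence of dose 1. Infection after the sample may be linked to a weak response. The remaining participants need not represent everyone given dose 1, so the post-dose-1 geometric mean may shift.

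The samples have no scheduled substitute. Appendix 2 lists humoral sampling at Visits 3 and 4 only for the double-blind Immunogenicity Subset. Section 9.2.2 says the subset is meant to show the magnitude and kinetics of the response.

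**Working it through.** **Step 1: the plan's own figure.** Table 3 has four groups with 50 vaccinees and 50 placebo recipients each. 8 × 50 = 400, which matches the N of 400 in Section 9.2.2, with 4 × 50 = 200 per arm.

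**Step 2: the rules side by side.**

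| Item | Rule | Place |
|---|---|---|
| Entry to PPI | both doses in the double-blind phase, judged per participant | population definitions after 9.2.4 |
| Analyses on PPI | all immunogenicity analyses | 9.5 |
| Timepoints summarised | all | 9.5.1 |
| Samples before dose 2 | baseline, 28 days after dose 1, pre-dose 2 | 8.1.4 |
| Dose 2 withheld | foreseen; immunogenicity follow-up continues | 7.1, 8.8 |
| Exception for samples before dose 2 | none stated | – |

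The footnote to the PPI definition covers out-of-window vaccination, not a missed dose. A dose 2 given after unblinding does not help either, because the definition requires both doses in the double-blind phase.

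**Step 3: precision.** The protocol gives no share f of vaccinees without a double-blind dose 2, so f is assumed. Retained n = 200 × (1 − f). Confidence interval width on the log scale is multiplied by 1/√(1 − f).

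| f (assumed) | n of 200 | per stratum of 50 | width factor |
|---|---|---|---|
| 10% | 180 | 45 | 1/√0.90 = 1.054 |
| 25% | 150 | 37.5 | 1/√0.75 = 1.155 |
| 40% | 120 | 30 | 1/√0.60 = 1.291 |

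These are upper limits for Day 29. They suppose that everyone without dose 2 has a usable Day 29 sample. Someone infected or unblinded before Day 29 does not.

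**Step 4: possible shift.** Let r be the post-dose-1 geometric mean in participants without dose 2 divided by that in participants with it. For all dose-1 recipients, log GM(all) = (1 − f) log GM(PPI) + f log[r × GM(PPI)]. Hence GM(PPI)/GM(all) = r^(−f). With r assumed between 0.67 and 1.5:

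| f (assumed) | r = 0.67 | r = 1 | r = 1.5 |
|---|---|---|---|
| 5% | 1.02 | 1 | 0.98 |
| 20% | 1.08 | 1 | 0.92 |
| 40% | 1.17 | 1 | 0.85 |

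If r = 1 there is no shift, and only the precision loss remains.

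**The case against.** The best defence is that a completer set is a legitimate choice. The double-blind phase evaluates a two-dose regimen, and following the same people from Day 29 to 14 days after dose 2 prevents a change in membership from looking like kinetics. That benefit is real, so it would be wrong to say the restriction gains nothing in validity. The protocol does not give this rationale, however. It already works at sample level after infection, and the concomitant-therapy text just before Section 6.11 makes exclusion from the immunogenicity analyses depend on when the therapy occurred. A completer display can sit beside a timepoint-specific set.

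A second defence is the FAS analysis, which needs only one dose. A reader might infer that the samples are discarded; they are not, only left out of the primary set. The remedy is partial: it covers key tables only, its certainty differs between two places, and it also readmits participants with major deviations, so it does not isolate this issue.

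Third, a reader might infer that the one-dose versus two-dose comparison is compromised. The documents do not support that. The direct comparison sits in open-label Subset B (Section 8.1.4, Table 4), and the footnote to the PPI definition confines that set to the double-blind phase.

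Fourth, a reader might apply the Step 3 losses equally to Day 57 and expect full recovery. Under Section 9.4.1 double-blind data stop at the unblinding visit, so anyone unblinded before Day 57 has no double-blind pre-dose-2 sample to restore. Samples after a confirmed infection stay excluded in any case.

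Finally, a large f and an r far from 1 need not occur together. Many missed doses could come from general unblinding, which has no obvious link to response, and Section 9.2.4 does not anticipate adverse events that preclude further vaccination.

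**Conclusion.** The point holds as a fault in the analysis-set definition, of modest size. Valid samples drawn before dose 2 are kept out of the primary descriptive summaries by a later event, and Section 7.1 ties that event partly to reactions to dose 1 and to infection. Under assumed non-receipt of 10%, 25% or 40%, Day 29 intervals widen by at most about 5%, 15% or 29%. Any shift in the geometric mean depends on an unknown response ratio and is nil if that ratio is 1. Sections 9.5 and 9.5.1 plan no formal immunogenicity testing, so no alpha, power or success criterion is involved. Restricting samples taken after dose 2 to two-dose recipients is proper.

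This reading rests on the second part of the protocol. Section 3 (objectives and endpoints), Section 6.4 (unblinding) and the SAP were not available. The PPI paragraph states the two-dose condition outright; what it leaves to the SAP is the list of major deviations and the open-label populations.

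**What to change.** Define the double-blind PPI set by timepoint, identically in both arms:

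- Samples up to and including pre-dose 2 require receipt of dose 1 and no impacting deviation or confirmed infection before that sample.
- Later samples require both doses, with the existing sample-level exclusions kept.

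Keep a same-participant display of two-dose completers as supportive for kinetics. State in one place whether the FAS repeat of key tables is certain or optional.

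The cost is one sentence in the population definition and a visit-level flag in the analysis dataset, with no new data. The set will then differ in membership across visits, so each table should show n by visit.
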